## 5.2 Treatment Regimen

### 5.2.1 OxyChip and fiducial placement

Fiducial(s) (one or two) may be implanted along with the OxyChip during the procedure at the discretion of the investigator. It is anticipated that fiducials will be used in most tumors, excepting those where superficiality and expected ease of OxyChip assessment make their use sub-optimal (for example for a, fungating skin tumor where the OxyChip is placed < 1 cm from the surface). Placement of the OxyChip and fiducials (if implanted) will occur via a **collaborative effort between the surgical oncologist and the PI or one of the co-investigators** with the following goals and protocol:

- (i) The OxyChip and fiducials will need to be removed in their entirety when the tumor is resected.
- (ii) The OxyChip will be positioned within the tumor and within 3 cm of the skin or mucosal surface.
- (iii) The selection of the specific site for insertion is guided (by available pre-operative MRI, CT, or PET imaging, or physical exam) to be inside the viable tumor and not in a necrotic core. All implantations will be performed with sterile technique with the skin prepped with alcohol or betadine and draped in a sterile fashion. The OxyChip and fiducials will be implanted by a minimally invasive, needle-based approach. The needle will be loaded by the provider injecting the OxyChip in the following order depending on what is determined to be implanted. Loading occurs immediately prior to implantation, in the sterile field:
  - a. OxyChip only: The needle is loaded with a single OxyChip.
  - b. One fiducial and OxyChip: The needle is loaded with both the fiducial and single OxyChip. Order within the needle for implantation is not significant; therefore, the fiducial may be loaded first into the needle and then the OxyChip or vice versa.
  - c. Two fiducials and OxyChip: The needle is loaded in the following order: one fiducial, the single OxyChip, then one fiducial.
- (iv) A local anesthetic will be offered to all patients prior to the implantation. After numbing, the loaded needle will be placed in the tumor guided by palpation (if sufficiently superficial and large), ultrasound, or a CT-guided procedure, and the needle contents will be deployed into the tumor using a stylet (Figure 6). The placement of the OxyChip may be performed by protocol trained Radiology staff or by protocol trained study personnel.

**Figure 6. OxyChip for implantation.** (A) The OxyChip, a cylindrical pellet that resembles a pencil lead, is prepared for loading into the needle for implantation. (B) The needle is loaded with a single OxyChip. When the needle tip is in the proper position in the tumor, the OxyChip is pushed into the tumor using the needle's stylet.

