### 1.3.6 EPR oximetry

EPR oximetry refers to the measurement of oxygen concentration by EPR spectroscopy. The basis of EPR oximetry is the physical interaction between molecular oxygen (O2) and paramagnetic material probes that are introduced into the tissue of interest. As O2 has two unpaired spins in the ground state, it can have an especially strong effect on the EPR spectra of the introduced probes. Discussion of interactions between the specific probes and O2 are given in several manuscripts devoted to characterization of chars and LiPc and derivatives. Briefly, if O2 approaches the probe within such proximity that there is appreciable overlap of the quantum mechanical wave functions of their unpaired electrons, then a spin-exchange interaction will occur. Under certain conditions which are met with the oxygen-sensitive materials, this exchange results in broadening of the spectral features through shortening of the relaxation times of the introduced paramagnetic material or reduction of existing exchange-narrowing, depending on the probe. When this broadening is calibrated against a range of gases of known pO2, the resulting calibration curve can be used to provide data on the oxygenation of the tissue surrounding the material. The fact that the widths of EPR resonance lines correlate with oxygen concentration has been used in a variety of biological settings.

The development of low-frequency EPR instrumentation at L-band (1-2 GHz) and even lower frequencies (600 MHz or 300 MHz) has made it possible to perform EPR oximetry measurements in animals and isolated functioning organs. Unfortunately, clinical EPR must confront the fact that the depth of penetration will continue to be a limiting factor, unless further advances in hardware design and their applications are successful. Generally speaking, noninvasive EPR measurements are limited to a penetration depth at the range of 1–2 cm at L-band (~1.2 GHz). Penetration depth can be increased to 8 cm or more by lowering the frequency to the 300-600 MHz range. The tradeoff, however, is that the signal-to-noise ratio significantly decreases at these lower frequencies, causing a decrease in spatial resolution and accuracy of pO2 measurements.

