## 1.4 EPR oximetry in human subjects using ink

[figure not shown]
We have demonstrated that oxygen measurements can be made in human subjects in superficial tumors using India ink. EPR oximetry measurements in human subjects were performed using a whole-body EPR spectrometer consisting of a 420-Gauss permanent magnet, magnetic field modulation and sweep coils, RF detection system including surface-loop resonators, and computer control. The spectrometer operates at an L-band frequency (~1.2 GHz), where a practical compromise between RF penetration depth and EPR sensitivity is achieved. At this frequency, RF penetration depths of approximately 10 mm are achieved. We have obtained pO2 data in superficial tumors at different sites in cancer patients and healthy volunteers. Our initial measurements in human subjects used India ink as an oxygen sensor and under conditions that could readily be incorporated into normal clinical processes. The ink was inserted into the tumors or other

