### 1.5.3 pO2 measurements

To date, we have made a total of >60 pO2 measurements. The pO2 values successfully measured (**Figure 7**) from the patients, on multiple visits, are shown in **Table 1**. In each session, where an EPR signal from the OxyChip could be detected, pO2 measurements were made continuously for 5-10 min while the patient breathed room air, followed by 10 min of breathing 100% oxygen, and then for 10 min after the patient had returned to room-air breathing. The tumor pO2 values showed varying degrees of hypoxia and response to hyperoxygenation (**Figure 8**). The EPR signal could not be detected in some patients. Ultrasound imaging revealed that the OxyChips in these tumors were deeper (10-16 mm) than the usual depth in other tumors, which may explain our inability to obtain an EPR signal.

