## **4 Subject Selection and Withdrawal**

### **4.1 Inclusion Criteria**

1. Phase 1A: Any tumor identified by imaging or physical exam to be accessible to OxyChip implantation and measurements and that is going to receive surgical resection with intent to remove the entire tumor. The tumor must be sufficiently large to accommodate the OxyChip.
2. Phase 1B: Any biopsy-proven malignancy expected to undergo neoadjuvant chemotherapy or radiotherapy prior to resection. The tumor must be sufficiently large to accommodate the OxyChip.
3. The tumor must be within 3 cm of the surface of the skin or mucosa.
4. Age  $\geq$ 18 years old.
5. Subject must be capable of giving informed consent
6. Anticipated time between implantation and planned surgical excision of at least three days.
7. Tumors must be  $\geq$  2.5 cm in minimum diameter to be eligible.

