## 5.2.3 Safety of EPR measurements

Our clinical EPR scanner shown in **Figure 7** operates at ~430 G (0.043 T) magnetic field strength and ~1.2 GHz microwave energy as the RF source. The field is very low compared to whole-body clinical MRI scanners that operate typically at 1.5T or 3T magnetic field strength. The 1.2 GHz RF source in our clinical EPR scanner will use <20-mW power continuously when turned on for a few minutes (2-5 minutes). The maximum specific absorption rate (SAR) in the tissue at the position that should have the greatest density of RF, directly under the loop of the surface-loop resonator, has been estimated to be  $3.7 \pm 1.2$  W/kg at 100 -mW incident 1.2 GHz RF power using a surface-loop resonator with an efficiency of about  $0.1 \text{ mT/W}^{1/2}$ . This estimated value is substantially below the recommended limit (12 W/kg) in the relevant regulation for

**Figure 7. Setup for EPR measurement of  $pO_2$  in human.** (A) A custom-designed and custom-built 400-Gauss whole-body magnet and coil assembly with a 50-cm gap to facilitate whole-body measurements of tissue oxygenation. (B) A head and neck cancer patient undergoing EPR measurement using a surface-loop resonator (shown by arrow) placed just above the tumor.

 Note that this is the same EPR scanner as used in the protocol CCRC D0626/CPHS #12459 previously approved by Full Committee Review of CPHS.

extremities. Thus, the SAR for our measurements, even at 100-mW power, is well within the acceptable range for human applications. The protocol for our clinical EPR scanner will not use rapidly changing magnetic field gradients such as those used in MRI. However, the EPR measurements use three types of magnetic fields that change in time during the measurement:

1. Main magnetic field sweep: The sweeping of the main magnetic field is done at slow rates, typically a linear sweep of 8 G over a 30-sec period, which translates to a rate of  $\sim 3 \times 10^{-5}$  T/sec.
2. Modulation field: We typically use a modulation field of 1 G or less at 20 kHz, which will amount to 2T/sec.
3. Multisite oximetry: We apply a static gradient magnetic field which will be applied during the entire 3-sec duration of data acquisition.

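### Chips may lie up to 3 cm deep, beyond every reach the protocol states at about 1.2 GHz, and the feasibility analysis cannot separate signal lost to depth from refusal or failure of the method

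*Combined protocol and SAP*

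**What the plan says.** **Permitted depth.** Inclusion criterion 3 in Section 4.1 reads: "The tumor must be within 3 cm of the surface of the skin or mucosa". Placement goal (ii) in Section 5.2.1 applies the same limit to the chip: "The OxyChip will be positioned within the tumor and within 3 cm of the skin or mucosal surface". For Phase 1A, inclusion criterion 1 also asks that the tumor be accessible to measurement, but attaches no depth. The Phase 1B criterion has no such condition.

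**Stated reach.** Section 5.2.3 says that the trial scanner "operates at ~430 G (0.043 T) magnetic field strength and ~1.2 GHz microwave energy as the RF source". Section 1.4 says of the earlier India-ink work, done at the same frequency: "At this frequency, RF penetration depths of approximately 10 mm are achieved". Section 1.3.6 gives a general L-band range of 1–2 cm. It mentions greater depths only for lower frequencies (300–600 MHz), at the price of a weaker signal.

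**Experience so far.** Section 1.5.3 reports: "The EPR signal could not be detected in some patients". It adds that the chips concerned "were deeper (10-16 mm) than the usual depth in other tumors, which may explain our inability to obtain an EPR signal". It does not say how many patients were affected.

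**Endpoint and analysis.** Section 3.3 defines the secondary endpoint as completing the oxygen measurements that were planned. Section 7.1 describes a qualitative judgement of whether measurements that were attempted succeeded, together with the time taken. No success threshold is set, and depth appears in neither place.

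**The concern.** Section 7.1 says the trial is meant to help design a larger study. Planners of that study will need to know why a reading was not obtained: the chip was too deep for the scanner, the patient declined, or the method failed within its range. These three reasons lead to different designs.

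The plan permits depths that its own text does not claim to be able to measure. It does not require chip depth to be recorded. It also describes feasibility with two different bases, planned sessions in Section 3.3 and attempted sessions in Section 7.1. A chip judged too deep to try counts against feasibility under the first and disappears under the second. The same data could therefore support quite different statements about feasibility.

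**Working it through.** The plan gives no feasibility rate, threshold or power calculation, so there is no figure of its own to reproduce. The check compares the depth statements and then asks what can be said about size.

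**Step 1. Permitted depth against stated reach.** Inputs: limit 30 mm (Sections 4.1 and 5.2.1); reach about 10 mm (Section 1.4); reach 10–20 mm (Section 1.3.6).

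- 30 / 10 = 3.0
- 30 / 20 = 1.5

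The limit exceeds the reach on either figure. Section 1.6 gives reasons for the larger cohorts, the longer implantation and the fiducials, but none for reading a chip at 2–3 cm at this frequency. The new EPR device designs and the fiducials (Sections 1.6.1 and 1.6.3) are described as helping to locate the chip; no gain in depth is stated.

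**Step 2. Reported losses.** Undetected chips lay at 10–16 mm. That is at or beyond the Section 1.4 figure but inside the Section 1.3.6 range. The two stated reaches therefore do not agree on whether these losses were to be expected, and without counts no failure rate by depth can be computed.

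**Step 3. How much non-completion could be due to depth.** Assumptions, none of them from the documents: a share d of chips is beyond reach and gives no signal; a share f of sessions is not completed for other reasons, independently of depth.

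- Completion over planned sessions = (1 − d)(1 − f)
- Share of non-completion due to depth alone = d(1 − f) / [1 − (1 − d)(1 − f)]

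| d | f | Completion | Share due to depth alone |
|---|---|---|---|
| 10% | 30% | 0.90 × 0.70 = 63% | 0.07 / 0.37 = 19% |
| 33% | 30% | 0.67 × 0.70 = 47% | 0.231 / 0.531 = 44% |
| 33% | 5% | 0.67 × 0.95 = 64% | 0.3135 / 0.3635 = 86% |
| 67% | 5% | 0.33 × 0.95 = 31% | 0.6365 / 0.6865 = 93% |

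The first and third rows show the problem. Overall completion is nearly the same (63% and 64%), yet depth explains 19% of the failures in one and 86% in the other. An overall result cannot distinguish them.

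**Step 4. Planned against attempted.** Take d = 33% and f = 10%, with f made up of attempts that fail. Over planned sessions, completion is 0.67 × 0.90 = 60%. If sessions on deep chips are not attempted and so drop out, success among attempts is 1 − 0.10 = 90%.

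**The case against.** The strongest reply is that 3 cm is a ceiling and not a typical depth. Section 1.5.3 says that the undetected chips were deeper than usual, and more than 60 measurements had been made, with values from 13 patients shown in Section 1.5.6. This stands, and it limits the claim. A reader might infer that most chips will be out of reach, for example by spreading depth evenly over 0–30 mm, and that the feasibility endpoint will mainly measure depth. The documents do not support that. They give no depth distribution, and what they do say suggests that depths of 10–16 mm were the exception. Part of Section 1.5 and the figures were not available for this review and may hold relevant data.

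It is also fair that the 10 mm figure belongs to an earlier spectrometer with a permanent magnet, whereas the trial scanner has an electromagnet (Section 5.2.2), and that Section 1.5.3 offers depth only as a possible explanation. It would be wrong to read the protocol as saying that a chip deeper than 10 mm cannot be measured. The gap between limit and reach remains, however, at the more generous 2 cm.

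Finally, Section 7.1 plans a qualitative assessment with no decision rule, and Section 3.1 lists optimizing measurement across anatomical sites among the aims. Finding where the signal fails is then a legitimate result. That is true, but it can be reported only if depth and the reason for each missing reading are known. Section 4.4.1 has reasons tracked when a patient asks to stop measurements. Nothing comparable covers absence of signal or sessions not attempted.

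**Conclusion.** The point holds in a limited form. The permitted depth exceeds every reach the protocol states at the trial scanner's frequency, by a factor of 1.5 to 3.0. The feasibility assessment does not separate signal lost to depth from refusal or from failure of the method, and its basis differs between Sections 3.3 and 7.1.

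The size of the effect is not known. Under the assumed ranges of d from 10% to 67% and f from 5% to 30%, depth alone accounts for 19% to 93% of non-completion. That range shows that the question is open; it is not a forecast.

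The consequence is confined to the secondary objective. The primary safety endpoint does not depend on readings, as the Section 3.1 schema says for both phases, and a chip that gives no signal still contributes safety data.

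**What to change.** 1. **Reconcile the depth statements** in Sections 1.3.6, 1.4, 1.5.3, 4.1 and 5.2.1, and say what reach is claimed for the trial scanner. No placement rule is proposed here; where a chip is placed is for the clinical team.
2. **Record chip depth** whenever ultrasound or CT is already used at placement or measurement, and the surface it is measured from. The limit may be counted from mucosa, while Section 5.2.2 puts the resonator on the skin.
3. **In Section 7.1, use planned sessions as the denominator**, in line with Section 3.3. Log the planned sessions for each patient in advance, because the Section 3.1 schema gives a minimum goal for Phase 1A and, during treatment in Phase 1B, only a weekly maximum. Classify each session as completed, no signal, declined or not attempted, with the reason.
4. **Report completion overall and by depth**: up to 10 mm, over 10 mm, not known. The 10 mm cut is for reporting only. Keep the overall result as the headline, since relying on the shallow group would select the favourable cases in a population eligible to 3 cm. State the depth range to which any feasibility conclusion applies.

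The cost is a few case report form fields and one table. Eligibility does not change and no imaging is added. The drawback is that depth will be missing for patients who are not imaged, for example after placement by palpation, so the group of unknown depth must be shown.

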## 5.2.2 Oxygen measurements

Patients will be positioned in the whole-body clinical EPR scanner located on the second floor of DHMC in Radiation Oncology (**Figure 7A**). The scanner is equipped with an electromagnet, and a translating bed, or chair, that facilitates rapid repositioning of measurement subjects. This magnet has a pole separation of 50 cm, suitable for measurement in humans.

An external loop resonator will be positioned on the skin surface (**Figure 7B**) above the OxyChip. Portable ultrasound may be used to assist in finding the OxyChip in order to facilitate the placement of this. Ultrasound imaging may be performed by trained Radiology staff or one of the trained study team members.

EPR measurements will be performed using standard data collection procedures, collecting multiple EPR spectra and converting the observed absorption linewidths to  $pO_2$  using pre-established calibration curves. If the patient agrees to breathing 100% oxygen, the measurement will be divided into three, continuous, approximately 10-minute time periods (Baseline- patient breathing room air, Hyperoxygenation- patient breathing pure (100%) oxygen, Recovery- patient return to breathing room air). If the patient is unwilling to breathe 100% oxygen, data associated with baseline tumor oxygen will be collected. Any measurement may be concluded prior to completion at any time at the discretion of the operator/physician/patient.

[figure not shown]
See Standard Method 68.x for further details regarding oxygen measurements.

The time from patient positioning to completion of the last measurement will be recorded for each reading.

Dartmouth's IRB, in reviewing two other protocols using the same clinical EPR scanner to make oxygen measurements (CPHS 12459 and CPHS16578), has previously determined that the EPR scanner presents a non-significant risk and therefore does not require an IDE process for its use for investigational purposes. See Standard Method 68.x for further details.)

## 5.2.3 Safety of EPR measurements

Our clinical EPR scanner shown in **Figure 7** operates at ~430 G (0.043 T) magnetic field strength and ~1.2 GHz microwave energy as the RF source. The field is very low compared to whole-body clinical MRI scanners that operate typically at 1.5T or 3T magnetic field strength. The 1.2 GHz RF source in our clinical EPR scanner will use <20-mW power continuously when turned on for a few minutes (2-5 minutes). The maximum specific absorption rate (SAR) in the tissue at the position that should have the greatest density of RF, directly under the loop of the surface-loop resonator, has been estimated to be  $3.7 \pm 1.2$  W/kg at 100 -mW incident 1.2 GHz RF power using a surface-loop resonator with an efficiency of about  $0.1 \text{ mT/W}^{1/2}$ . This estimated value is substantially below the recommended limit (12 W/kg) in the relevant regulation for

**Figure 7. Setup for EPR measurement of  $pO_2$  in human.** (A) A custom-designed and custom-built 400-Gauss whole-body magnet and coil assembly with a 50-cm gap to facilitate whole-body measurements of tissue oxygenation. (B) A head and neck cancer patient undergoing EPR measurement using a surface-loop resonator (shown by arrow) placed just above the tumor.

 Note that this is the same EPR scanner as used in the protocol CCRC D0626/CPHS #12459 previously approved by Full Committee Review of CPHS.

extremities. Thus, the SAR for our measurements, even at 100-mW power, is well within the acceptable range for human applications. The protocol for our clinical EPR scanner will not use rapidly changing magnetic field gradients such as those used in MRI. However, the EPR measurements use three types of magnetic fields that change in time during the measurement:

1. Main magnetic field sweep: The sweeping of the main magnetic field is done at slow rates, typically a linear sweep of 8 G over a 30-sec period, which translates to a rate of  $\sim 3 \times 10^{-5}$  T/sec.
2. Modulation field: We typically use a modulation field of 1 G or less at 20 kHz, which will amount to 2T/sec.
3. Multisite oximetry: We apply a static gradient magnetic field which will be applied during the entire 3-sec duration of data acquisition.

In all three scenarios, the rate of change of the magnetic field is well below the limit of 20 T/sec set by the 1988 or 1995 Magnetic Resonance Diagnostic Devices (MRDD) Guidance. Hence the time-rate of change in the magnetic field is not expected to have any significant effect on the subject.

#### 5.2.4 OxyChip and Fiducial removal

The OxyChip and fiducial(s) will be excised with the surgical specimen. The surgeon determines the timing of surgery, but it will typically be planned to be within 4 weeks for Phase 1A, or after completion of radiotherapy or chemotherapy for Phase 1B, although the OxyChip may remain implanted for up to 52 weeks for both Phases (excluding the first 6 patients enrolled into Phase 1A). The minimum time from implantation to surgical excision required for inclusion is 3 days. Note, patients in Phase 1B are expected to have the OxyChip in place for a minimum of 5 weeks (the expected duration of radiation therapy). The protocol and goals for removal will be as follows:

- (i) All attempts will be made to maintain the OxyChip in the tissue specimen, without disrupting the shape or position within the tumor mass.
- (ii) In collaboration with the surgeon, after the patient has been anesthetized, imaging of the fiducial(s) will occur prior to surgery in order to identify the putative location of the OxyChip and facilitate surgical removal.
  - a. We anticipate the fluoroscopy will be sufficient for identification of the fiducial prior to surgical removal (and after). However, due to concerns that more advanced imaging may be necessary, the first three patients with fiducial implantation will have their surgery performed at DHMC in the Center for Surgical Innovation (CSI). If fluoroscopy is sufficient for identification, then subsequent surgeries can be performed in standard operating rooms as desired if fluoroscopy is available for identification of fiducials before and after surgery.
    - i. In the first three patients in the CSI, if the fiducial is not found prior to surgery either CT or MRI imaging will be performed to identify the fiducials. If the fiducials are found within the expected surgical field, or reasonably adjacent, fiducials will be removed during surgery. If the fiducials are found in an unanticipated area, consultation between the PI and the surgeon will occur as to whether surgical resection is acceptable. All decisions regarding surgery will be at the discretion of the surgeon. If no fiducials are found after advanced imaging prior to surgery, then surgery will proceed as planned as all reasonable measures will have been taken to identify the location of the OxyChip at that time.
  - b. After surgical resection, fluoroscopy will be performed on the specimen prior to surgical closure in order to ensure that the fiducials have been removed. If the fiducials are present in the specimen, it is highly likely that the OxyChip has been removed and surgical closure will occur. If the fiducials are not found then advanced imaging via CT or MRI will occur to attempt to identify the fiducials in the patient. If the fiducials are then identified, in consultation with the surgeon, that area will be removed if it is deemed acceptably close to the surgical field. If the fiducial is not visualized, a discussion will be had with the surgeon regarding further excisions of margins, as well as a search of the surgical field for an

OxyChip/fiducial that may have fallen out at the time of surgery. In this circumstance, all attempts will be reasonably made to ensure removal of the OxyChip, but the surgeon will have discretion about what is clinically appropriate.

If a definitive surgery is deemed unnecessary after chemotherapy therapy or radiotherapy (Phase 1B), or if a definitive surgery is delayed beyond the expected time point (> 52 weeks) due to unforeseen circumstances, the OxyChip may be removed in a minor procedure under local anesthesia. The OxyChip will be identified using the fiducials as surrogates via ultrasound or fluoroscopy, and that area will be excised using similar considerations noted above. This procedure will be performed at the first available time deemed safe for the patient as determined by the primary oncology team.

In the circumstance where a patient dies prior to surgery and the OxyChip is still in place, a discussion will be had with the next of kin regarding removal of the OxyChip prior to burial. If next of kin agrees to allow OxyChip removal, it may be removed via a small surgical procedure.

